## 11.3 SAFETY ANALYSIS

### 11.3.1 PRIMARY SAFETY ENDPOINT

As described above a statistical test based on the Poisson distribution will be performed to investigate whether the linearized yearly rate for each cardiovascular adverse event (thromboembolism, all hemorrhage, all perivalvular leak, and endocarditis) is less than 2 times the appropriate OPC from the 1994 Draft Heart Valve guidance.

For reporting purposes, the percent of subjects who experience an early adverse event within 30 days of implant will be summarized. Linearized rates will be used to summarize adverse events for the late (>30 days) post-operative period. The linearized rates will be reported as the number of events occurring after the early post-operative period per year of subject survival. In addition, the linearized rate and 30-day frequency for thromboembolism will be stratified by concomitant cardiac problems (atrial fibrillation, sinus rhythm, pacemakers, etc.).

Accounting for both early and late post-operative events, actuarial analysis according to Kaplan-Meier will be used to show estimated probability of freedom from each adverse event.

### 11.3.2 SECONDARY SAFETY ENDPOINTS

#### **Blood Data**

Blood data (red blood count, white blood count, hematocrit, hemoglobin, platelet count, serum lactate dehydrogenase, haptoglobin, and reticulocytes) will be collected preoperatively, at 6-months and annually post implant. This blood data will support the absence / presence of related adverse events; in particular hemolysis. Data will be reported as the percent of subjects with results within the normal ranges at each time interval. The percent of subjects with hemolysis at each point will also be reported. Summaries will be presented for the entire study cohort and will also be stratified by valve size.

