#### **4.2.2 SECONDARY SAFETY ENDPOINTS**

Descriptive information of early rates, late linearized rates and actuarial analysis of the following:

- Thromboembolism
- Valve thrombosis
- All hemorrhage
- Major hemorrhage
- All perivalvular leak
- Major perivalvular leak
- Endocarditis
- Hemolysis
- Structural valve deterioration

- Non-structural valve dysfunction
- Reoperation
- Explant
- Death
- Valve-related death

Blood Data (white blood count, red blood count, hematocrit, hemoglobin, platelet count, serum lactate dehydrogenase, haptoglobin and reticulocytes).

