## 8.1 PREOPERATIVE PROCEDURES

The investigator will determine and record each subject's demographics (date of birth, sex), physical assessment (heart rate, height, weight and blood pressure), New York Heart Association (NYHA) functional class, cardiac rhythm, cardiovascular medical history/risk factors, non-cardiovascular conditions, previous cardiovascular procedures/interventions, anti-thromboembolic medications and coagulation profile.

Blood data is required for each subject preoperatively and should be collected within 30 days prior to valve replacement. The following parameters will be collected: white blood cell count (WBC), red blood cell count (RBC), hemoglobin, hematocrit, reticulocytes, platelet count, haptoglobin and serum lactic dehydrogenase (SLDH). Should the serum LDH be elevated, it should be fractionated. Preoperative data is indicated on the CRF and is outlined in Table 2. The investigator or designee will also indicate if the parameters are within normal ranges or not and whether the change is clinically significant. A QOL survey (EQ-5D) will be completed by the subject pre operatively.

In addition, pre-operative echocardiographic evaluation is optional for this study; however if performed, the investigator should document the findings. The echocardiography information will be indicated on the CRF.

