### 8.3.2 POSTOPERATIVE FOLLOW-UP VISITS

Post operative follow-up visits are required at 6 months, 1 year, and annually thereafter for a minimum of 8 years. In addition to the requested data at discharge, the New York Heart Association (NYHA) functional class will be assessed at subsequent postoperative assessments at 6-months (between 3-6 months) and annually post implant ( $\pm$  1 month of annual follow-up evaluations).

Postoperative blood studies are also required at 6- months (between 3-6 months), Blood data will support the absence/presence of related adverse events; in particular hemolysis. Should the serum LDH be elevated, it should be fractionated. The investigator or designee will also indicate if the parameters are within normal ranges or not and whether this poses a clinically significant event. The investigator will document all clinically significant events by completing the appropriate adverse event CRF.

Full Doppler/echocardiography is required for all subjects at 6-months (between 3-6 months) at 1, 5 and 8 year follow-up visits. At 2, 4 and 6 year follow-up visits, an echocardiography with regurgitation data, if present; ejection fractions, gradients, EOA, LV Mass and perivalvular leaks will be obtained. The echocardiography information will be indicated on the CRF. The investigator will document all clinically significant regurgitation and stenosis that need intervention by completing the appropriate adverse event CRF.

A QOL survey (EQ-5D) will be completed by the subject preoperatively and at the 6-month follow-up visit.

The assessment of cardiovascular adverse events will be conducted in accordance with the revised "Guidelines for Reporting Morbidity and Mortality after Cardiac Valvular Operations" (STS guidelines) published by the Society for Thoracic Surgeons (STS) in September 1988 [3] and revised in 2008 [4] [REDACTED]. All pertinent details related to the adverse event and evaluation of valve relatedness will be completed in accordance with the revised STS guidelines. In reporting adverse events, the clinical investigator will assess all cardiovascular related

symptoms including abnormal heart murmur, shortness of breath, exercise intolerance, dyspnea, orthopnea, anemia, fever, arrhythmia, transient ischemic attack, stroke, paralysis, low cardiac output, pulmonary edema, congestive heart failure and myocardial infarction as to their relation to the valve and will complete the appropriate adverse event data form as needed.

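### The blood-marker summary in 11.3.2 drops the direction of abnormality and the subject's own pre-operative value, so it cannot cross-check the separately reported hemolysis events

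*Combined protocol and SAP*

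**What the plan says.** Section 4.2.2 lists blood data as a secondary safety item alongside the event endpoints. Section 11.3.2 (Blood Data) says the markers "will be collected preoperatively, at 6-months and annually post implant" and gives their purpose: "This blood data will support the absence / presence of related adverse events; in particular hemolysis". The marker-level analysis is one sentence: "Data will be reported as the percent of subjects with results within the normal ranges at each time interval". Two further sentences complete the paragraph: "The percent of subjects with hemolysis at each point will also be reported", and "Summaries will be presented for the entire study cohort and will also be stratified by valve size".

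A pre-operative result is mandatory. Section 8.1 states: "Blood data is required for each subject preoperatively and should be collected within 30 days prior to valve replacement". Under Section 8, each site supplies its own list of normal values.

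Hemolysis is also an event endpoint. It is in the Section 4.2.2 list introduced by "Descriptive information of early rates, late linearized rates and actuarial analysis of the following", and Section 8.3.2 gives it an adverse event form. That section also describes how a post-operative result can become an event: "The investigator or designee will also indicate if the parameters are within normal ranges or not and whether this poses a clinically significant event". If it does, the event form is completed.

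**The concern.** The stated use of the markers is directional. Hemolysis shows as low haptoglobin and raised LDH, and the protocol itself treats LDH in one direction only, since it is fractionated when elevated. A single in-range percentage counts a high haptoglobin the same as a low one, and a low LDH the same as a high one.

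The figure is also a separate cross-section at each visit. A subject abnormal before surgery and unchanged afterwards looks the same as one who became abnormal after implant. The people in the columns change too, through death, loss to follow-up and exit after explant (Section 10.5).

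At stake is the value of the laboratory data as an independent check. In the visible text, a hemolysis event depends on an investigator judging a result clinically significant and filing a form. A drift toward hemolysis that no investigator judged significant would have to be seen in the marker table, and that table removes direction and within-subject change.

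**Working it through.** The plan states no sample size, threshold or expected distribution for the blood data, so there is no figure to reproduce. The check has four parts. The marker counts and prevalences are assumed; 101, 225, 60% and 15% come from the plan.

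**1. Direction (assumed counts, n = 101, the 8-year target in Section 5).**
- Before surgery: 10 low, 10 high, 81 within range. In range = 81/101 = 80.2%; high = 10/101 = 9.9%.
- At follow-up: 0 low, 20 high, 81 within range. In range = 81/101 = 80.2%; high = 20/101 = 19.8%.
- The planned figure is unchanged although high values have doubled. For LDH, that is the direction of interest.

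**2. New abnormality (assumed counts, same 101 subjects at both times).**
- Before surgery: 20 out of range, 81 within range.
- At follow-up all 20 have normalized, and 20 of the 81 have become abnormal: 20/81 = 24.7%.
- In range = 81/101 = 80.2% both times. Only a paired table shows the 24.7%.

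**3. Who is in each column (Section 11.1 inputs).**
- Implanted: 225. Assumed 8-year survival: 60%. Allowance for loss to follow-up: up to 15%.
- Survivors before any loss: 225 × 0.60 = 135, or 60% of those implanted.
- After 15% loss: 135 × 0.85 = 114.75, or 51%.
- At the secured minimum: 101/225 = 44.9%.
- On the plan's own assumptions, the 8-year column therefore describes roughly 45% to 60% of the subjects in the pre-operative column. The two can differ without any subject's result changing.

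**4. Does the separate hemolysis percentage suffer the same loss?** No. It counts subjects with hemolysis, so merging high and low marker values does not touch it. If 101 subjects are assessed and every case is identified, the chance of seeing at least one is 1 − (1 − p)^101:

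| Assumed prevalence p | Chance of at least one case |
|---|---|
| 1% | 63.8% |
| 2% | 87.0% |
| 3% | 95.4% |
| 5% | 99.4% |

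The condition that every case is identified is where a directional marker table would help, because it does not depend on the investigator's classification.

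**Comparison within the plan.** For echocardiography, Section 11.4 specifies change from baseline and paired tests at one year, although the pre-operative echo is optional. For blood data, where the pre-operative sample is mandatory, it specifies neither.

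**The case against.** The strongest reply is that the plan detects hemolysis by another route. The sentence after the marker summary promises the percentage with hemolysis at each point. Section 4.2.2 adds early, late linearized and actuarial rates, and Section 11.3.1 adds Kaplan-Meier freedom from each adverse event. Investigators review each result for range and clinical significance, and raised LDH is followed up. The marker table is supportive only.

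This stands, and it rules out a stronger reading. A reader who stops at the marker sentence might infer that the plan cannot show hemolysis, or that the secondary safety question goes unanswered. The documents do not support that. Nor does the shrinking denominator of the marker table carry over to the event analyses, which count events occurring before death or exit.

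It is also fair to say that the counts above are assumed and that exact cancellation is not to be expected. They show what the table cannot distinguish, not what will happen. A changing denominator is common to any by-visit table in a long study, and nothing in 11.3.2 presents the columns as a formal test of change.

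Finally, the visible text gives no laboratory criterion for hemolysis, but it refers to published reporting guidelines and some accompanying material is redacted. The absence of a visible criterion should not be counted as a gap in the plan.

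The reply does not show that the marker table can do its supporting job. Data meant to support the presence or absence of hemolysis should show whether results moved in the hemolytic direction, in the same subjects, after implant.

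**Conclusion.** The point holds in a limited form. The Section 11.3.2 marker summary cannot show directional or newly arising abnormality, so it adds little to the hemolysis reporting and cannot serve as an objective check on investigator-classified events. The hemolysis signal itself remains in the plan through the separate percentage and the event rates.

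The practical size cannot be computed, because the documents give no marker distributions. The examples show only that a constant 80.2% is compatible with a doubling of high values or with 24.7% of previously normal subjects becoming abnormal. Severity is minor: the summary is descriptive, and no primary test, sample size or error rate depends on it.

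The conclusion assumes that no further marker table is specified in text not available for review. It also assumes that blood is drawn annually, as the Study Procedures Chart, Table 5 and 11.3.2 indicate; the blood-study sentence in Section 8.3.2 names only the 6-month sample.

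**What to change.** In Section 11.3.2, replace the single in-range percentage with two displays, each overall and by valve size:

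1. For each marker and visit, the number and percentage of subjects below, within and above the site's normal range, with the number assessed.
2. For each marker and post-operative visit, a shift table from the subject's own pre-operative category to the category at that visit, restricted to subjects with both results.

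Keep the planned percentage with hemolysis beside them, so that the laboratory pattern and the classified events can be read together. The shift table also deals with the changing denominator, because each table compares the same people at two times.

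No new samples or visits are needed. Pre-operative and follow-up results and site normal ranges are already to be collected, assuming the case report form records the result and not only an in-range flag. The cost is SAP wording and a few more descriptive tables. Some valve-size strata will have small cells, so counts should be shown with the percentages and no testing added.

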### **Time to Death, Reoperation, and Explant**

Time to death from the date of operation will be analyzed by the method of Kaplan and Meier. Time to reoperation from the date of operation as well as time to explant from the date of reoperation will be similarly analyzed. For time to explant and time to reoperation, the time to *first* explant or reoperation will be calculated for those subjects requiring explant or reoperation. These analyses will also be reported stratified by valve size. Analyses for time to explant and time to reoperation will also be stratified by fatal versus non-fatal events.

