The investigator will record adverse events on the adverse event CRF. The different adverse event CRFs are designed to capture relevant information for thromboembolism, valvular thrombosis, non-structural valve dysfunction, structural valve deterioration, bleeding events, endocarditis, hemolysis and all other adverse events respectively. Perivalvular leaks will be captured as part of the non-structural valve dysfunction adverse event data form. The outcome/resolution status of the adverse event will also be indicated as part of the adverse event data form. If an event results in death, copies of the autopsy report and/or death summary must be sent to Edwards, as permitted by local laws. Details of expiration and re-operation / explant data will be documented on CRFs. The investigator will make every effort to return the explanted valve(s) (at autopsy or explantation) to Edwards (Section 10.5).

It is recommended to maintain bioprosthetic heart valve recipients on anticoagulant therapy during the initial healing stages after implantation (approximately two to three months) except where contraindicated. The appropriate anticoagulation therapy must be determined by the physician on an individual basis and based on current ACC/AHA guidelines [5].

At each postoperative assessment, the investigator should determine the subject's availability for future follow-ups. The requested clinical, blood data and echocardiography variables postoperatively are collected on the CRFs provided and are outlined in Table 5 below.

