### **Hemodynamic Performance**

Echocardiography data will be obtained preoperatively, early postoperatively and/or discharge, at 6-months and at 1, 5 and 8 year follow-ups. Descriptive statistics for the continuous echo variables and change from baseline (e.g. mean, standard deviation, and range) will be categorized by time interval and size. Regurgitation data will be summarized using frequency at each severity level.

Improvement in regurgitation at one year will be analyzed via the Jonckheere-Terpstra [11] test. Change at one year from baseline for all other hemodynamic outcomes will be analyzed using paired *t*-tests.

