## 11.6 MISSING DATA

All statistical tests on the effectiveness endpoints will be performed in two ways: (1) using only those subjects with available required for endpoint analysis and (2) by using the method of last observation carried forward (LOCF). Both methods of analyses will then be compared. However, both methods will be used for the comparison of NYHA classification at 8 year post implant to OPC (75%) and for the comparison of hemodynamic performance one year to baseline for the purpose of investigating the effect of loss-to-follow-up.

NYHA classification and hemodynamic performance will be summarized at each of the follow-up interval. In addition, the NYHA classification will only be statistically compared to OPC at 8 years post implant and only the one year post implant hemodynamic performance will be statistically compared to baseline.

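### Time to explant is given the reoperation date as its start, probably a slip for the operation, and the one-year regurgitation test is an independent-groups test with no groups or baseline defined

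*Combined protocol and SAP*

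**What the plan says.** **Time to explant.** Section 11.3.2 (Time to Death, Reoperation, and Explant) states "Time to death from the date of operation will be analyzed by the method of Kaplan and Meier". It starts time to reoperation at the operation as well. For explant it then says "time to explant from the date of reoperation will be similarly analyzed" and gives no reason for the different start. The next sentence says that times to first explant or reoperation are calculated for the subjects who need one. Section 4.2.2 promises "Descriptive information of early rates, late linearized rates and actuarial analysis of the following", and explant is on that list beside death and reoperation.

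**Regurgitation at one year.** Section 11.4 (Hemodynamic Performance) states "Improvement in regurgitation at one year will be analyzed via the Jonckheere-Terpstra" test and names no grouping factor. The next sentence reads "Change at one year from baseline for all other hemodynamic outcomes will be analyzed using paired" t-tests. Section 11.6 describes the analysis as being "for the comparison of hemodynamic performance one year to baseline" and adds that "only the one year post implant hemodynamic performance will be statistically compared to baseline".

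**Baseline echo.** Neither Section 11.4 nor Section 11.6 says which examination is baseline. The preoperative echo is optional (Section 2 chart, Section 8.1). An early postoperative or discharge echo is required (Section 8.3.1).

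**The concern.** For explant, the start date decides who is at risk. A curve that starts at reoperation describes what happens to the few subjects who are reoperated. It does not estimate freedom from explant after implantation, which is the durability result an 8-year valve study needs and which Section 4.2.2 lists.

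For regurgitation, the named test does not fit the question. Jonckheere-Terpstra looks for an ordered trend across independent groups, whereas the plan asks whether the same subjects improved from baseline. An analyst would have to choose the groups after the fact. Using visits as groups discards the pairing. Using valve sizes as groups tests a trend across sizes, which is not improvement. The unnamed baseline adds a second open choice. A preoperative echo grades the valve that was removed, so the comparison is old valve against study valve. A discharge echo makes it study valve over time. This choice affects the paired t-tests too.

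**Working it through.** The plan gives no sample size, power or error calculation for either analysis, so there is no figure of its own to reproduce. The sizes below rest on assumed inputs, labelled as such.

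**(a) Who has a start date under the literal wording**

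Inputs: 225 implanted (Section 5) and 60% 8-year survival (Section 11.1). Assumed: cumulative reoperation by year 8, ignoring death, of r = 3%, 5% or 10%, with constant hazards.

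- Hazards: hd = -ln(0.6)/8 for death and hr = -ln(1 - r)/8 for reoperation.
- Share reoperated before death by year 8 = hr/(hr + hd) × (1 - exp(-8(hr + hd))).
- For r = 5%: 8hd = 0.5108 and 8hr = 0.0513. The share is 0.0513/0.5621 × (1 - 0.60 × 0.95) = 0.0912 × 0.43 = 0.0392, and 225 × 0.0392 = 8.8 subjects.

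| Assumed r | Reoperated, 60% survival | No start date | Reoperated, 80% survival (assumed) | No start date |
|---|---|---|---|---|
| 3% | 5.3 | 98% | 6.1 | 97% |
| 5% | 8.8 | 96% | 10.1 | 96% |
| 10% | 17.7 | 92% | 20.2 | 91% |

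A second illustration, ignoring death, shows the effect on the curve. Assume reoperation at 1% per year, with 50% to 100% of reoperations being explants. About 225 × (1 - exp(-0.08)) = 17 subjects are reoperated. Counted from the operation, 8-year freedom from explant is exp(-0.04) = 96% down to exp(-0.08) = 92%. Counted from the reoperation, only those 17 are ever at risk, and the curve falls to between 50% and 0% at time zero.

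Explants at autopsy, which Section 10.5 foresees, have no start date if the subject was never reoperated.

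**(b) Regurgitation test with the two visits as groups**

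With two groups, Jonckheere-Terpstra is the Mann-Whitney test. It was compared with the tie-corrected Wilcoxon signed-rank test by simulation. Assumptions:

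- Five ordered grades cut from bivariate normals, with class shares of 20% each, 30/25/20/15/10%, or 60/25/10/4/1%.
- 60, 101 or 150 pairs, at one-sided 5%.
- 20,000 data sets for size and 10,000 for power.

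Ranges run across the three grade distributions and, for size, the three pair counts.

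| Correlation | Size, unpaired | Size, paired | Power, unpaired* | Power, paired* |
|---|---|---|---|---|
| -0.3 | 6.5-7.3% | 4.8-5.3% | – | – |
| 0 | 4.9-5.3% | 4.8-5.3% | 55-65% | 54-65% |
| 0.3 | 2.6-3.3% | 4.7-5.2% | 56-67% | 62-76% |
| 0.6 | 0.8-1.4% | 4.9-5.2% | 57-72% | 78-91% |

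*Shift of 0.25 SD, 150 pairs.

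- At correlation 0.6 with 101 pairs, power for the same shift is 40-51% unpaired against 64-79% paired.
- At 0.5 SD with 150 pairs and correlation 0 or above, both tests reach at least 96%.
- Two-sided, the unpaired size is 2.1-2.7% at correlation 0.3 and 0.4-0.8% at 0.6.

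As a check, the unpaired size should be close to Φ(-1.645/√(1 - r)), with r here the rank correlation of the observed grades. This gives 3.3% at r = 0.2, 2.5% at 0.3 and 1.0% at 0.5, in line with the simulation.

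**The case against.** **Explant.** Most readers would recognize the wording as a slip, so the 91-98% figures size a reading that few analysts would follow. Section 11.3.1 also promises Kaplan-Meier freedom from each adverse event, covering early and late events, with early defined from implant, and Section 9 lists explant among possible adverse events. An implant-origin curve is therefore arguably already planned. This lowers the risk but does not remove the conflict. Section 11.3.1 is a general sentence under the primary safety heading, while Section 11.3.2 is the specific rule and the only place that sets a start date for explant. Section 8.3.2 says "Details of expiration and re-operation / explant data will be documented on CRFs", but a form layout does not show that explants occur on the reoperation date. The time-zero point rests on surgical logic.

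**Regurgitation.** The declared hemodynamic endpoint in Section 4.2.4 is at 8 years, so the one-year test is supplementary. Harm is limited: size is conservative under positive correlation, nothing is lost at zero correlation, and both tests do well for a 0.5 SD shift with 150 pairs. The documents support neither a correlation of 0.6 nor a shift of 0.25 SD. If baseline is the preoperative echo, a correlation near zero cannot be excluded. If it is the required discharge echo, about 200 pairs is plausible (assumed), and at correlation 0.6 and 0.25 SD power is then about 70-86% against 88-96%, a smaller gap. Another possible grouping is one-year grade across ordered baseline grades, but that tests association, not improvement.

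These points bear on weight. They do not supply the missing groups or baseline, and they do not correct the start date.

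**Conclusion.** The concern holds on both parts. The explant start date is wrong as written for the endpoint it serves. Under the assumed reoperation rates of 3% to 10%, it leaves out 92-98% of implanted subjects at 60% survival and 91-97% at 80%. The conclusion does not depend on the exact rate, because anyone never reoperated is left out. Only the sponsor can confirm that the operation was meant.

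The regurgitation test cannot be run without a choice of groups and baseline that the plan does not make, and no obvious grouping gives a sound test of improvement within subjects. With visits as groups there is no excess of false positives unless the correlation is negative. The cost is power, up to roughly 20 to 30 percentage points in the cases tabulated at correlation 0.6 and a 0.25 SD shift, and none at zero correlation.

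Both are secondary matters that should be corrected before analysis. The primary safety and effectiveness tests and the sample size are untouched.

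**What to change.** **Section 11.3.2.** Define time to explant from the date of the implant operation, for all implanted subjects. Censor those without explant at death or last follow-up. Reword the next sentence, on times for subjects who need explant or reoperation, so that it cannot be read as dropping event-free subjects from the curves.

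**Section 11.4.** Replace Jonckheere-Terpstra with one named paired ordinal test of the one-year grade against baseline in the same subjects, either Wilcoxon signed-rank or marginal homogeneity, and state whether it is one- or two-sided. State which echo is baseline for all hemodynamic comparisons. If it is the optional preoperative echo, report the number of pairs and label the result as applying to that subset. The restriction of hemodynamic testing to one year in Section 11.6 can stay.

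**Cost.** One phrase and a consistent rewording of the adjacent sentence in Section 11.3.2, and two or three sentences in Section 11.4. No new data are needed, since implant, explant and death dates and echo grades are already collected.

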### **Nonstructural Valve Dysfunction and Structural Valve Deterioration**

The percentage of subjects experiencing nonstructural valve dysfunction and structural valve deterioration within the early post-operative period (within 30 days of implant) will be reported. Linearized rates will be used to summarize nonstructural valve dysfunction and structural valve deterioration for the late (>30 days) post-operative period. The linearized rates will be reported as the number of nonstructural valve dysfunctions and structural valve deteriorations occurring after the early post-operative period per year of subject exposure. The 30-day frequency and linearized rate for nonstructural deterioration and structural dysfunction will be stratified by the nature of the dysfunction.

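### Splitting the reoperation and explant curves by fatal versus non-fatal event is under-specified: read literally each curve ends at 0%, and read as event types Kaplan-Meier overstates each type's 8-year risk

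*Combined protocol and SAP*

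**What the plan says.** The paragraph on time to death, reoperation and explant in Section 11.3.2 sets the method through time to death: "Time to death from the date of operation will be analyzed by the method of Kaplan and Meier". It continues: "Time to reoperation from the date of operation as well as time to explant from the date of reoperation will be similarly analyzed". Only the first explant or reoperation counts, and that time "will be calculated for those subjects requiring explant or reoperation". Two breakdowns follow. The first is "These analyses will also be reported stratified by valve size". The second is "Analyses for time to explant and time to reoperation will also be stratified by fatal versus non-fatal events".

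The paragraph does not say whether the second breakdown divides subjects or event types. It does not say how the other event type, or death without the event, is handled, and it does not define a fatal reoperation or explant. Section 10.4 requires deaths to be reported for 30 days after explant, but that is a reporting rule.

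Section 4.2.2 lists reoperation and explant among the secondary safety endpoints under "Descriptive information of early rates, late linearized rates and actuarial analysis of the following". No hypothesis test is attached to them.

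**The concern.** A Kaplan-Meier stratum fixes who is at risk from time zero. Valve size can do that because it is known for every implanted subject. Fatality of the event cannot, because it does not exist until the event occurs. The two breakdowns stand in consecutive sentences with the same verb, and the preceding sentence refers only to subjects who had the event. A programmer could therefore build the fatal and non-fatal groups as the valve-size groups are built. The output would show when events happened among those who had one, under a label suggesting freedom from the event.

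The event-type reading avoids that but leaves a second question. In a cohort expected to lose about 40% to death by 8 years, treating death as ordinary censoring gives a larger figure than the proportion of patients who actually have the event. The plan does not say which quantity it wants.

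**Working it through.** The plan gives no figure for this breakdown, so there is none to reproduce. The check compares the readings under constant hazards, with complete follow-up to 8 years.

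**Inputs**
- 8-year survival 60% (Section 11.1). Death hazard d = -ln(0.60)/8 = 0.5108/8 = 0.06385 per year. It is used here as the hazard of death without reoperation, a slight simplification.
- Implants: 225 (Section 5).
- Reoperation hazard r = 0.5%, 1% or 2% per year, and fatal share f = 5%, 10% or 20%. The documents give neither; both are assumptions.

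**Literal reading (strata of subjects), r = 1%, f = 10%**
- Total hazard h = 0.06385 + 0.01 = 0.07385, and exp(-8h) = 0.5539.
- Share of subjects with a first reoperation by 8 years: (r/h)(1 - exp(-8h)) = 0.1354 × 0.4461 = 6.0%, of which 0.6% are fatal and 5.4% non-fatal. The other 94% fit neither stratum.
- Among those with the event, the proportion still free at t is (exp(-ht) - exp(-8h))/(1 - exp(-8h)). This is 0.84 at 1 year, 0.43 at 4 years and 0 at 8 years. Under these assumptions it is the same for both strata and says nothing about how often the event occurs.

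**Event-type reading (all subjects at risk), r = 1%, f = 10%**
- Kaplan-Meier freedom from fatal reoperation: exp(-8 × 0.001) = 0.992.
- Kaplan-Meier freedom from non-fatal reoperation: exp(-8 × 0.009) = 0.931.
- Product: 0.923 = exp(-8 × 0.01), the freedom from any reoperation. The curves are coherent.
- One minus Kaplan-Meier, non-fatal: 6.9%. Cumulative incidence with death and the other type competing: 0.9 × 6.04% = 5.4%.

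**Across reoperation rates, at f = 10%** (8-year risk)

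| r per year | Non-fatal, 1 - KM | Non-fatal, cumulative incidence | Ratio | Fatal, 1 - KM | Fatal, cumulative incidence | Ratio |
|---|---|---|---|---|---|---|
| 0.5% | 3.54% | 2.77% | 1.28 | 0.399% | 0.308% | 1.30 |
| 1% | 6.95% | 5.44% | 1.28 | 0.797% | 0.604% | 1.32 |
| 2% | 13.41% | 10.49% | 1.28 | 1.587% | 1.166% | 1.36 |

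The relative overstatement of the non-fatal risk barely moves with the assumed reoperation rate, because it comes mainly from the 60% survival.

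**Event counts in 225 subjects.** At r = 1%, f = 10%: 225 × 0.0604 = 13.6 first reoperations, 1.4 of them fatal. Over the whole grid: about 7 to 26 reoperations, 0.3 to 5 fatal.

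**Explant.** Its clock starts at reoperation, so a subject never reoperated has no time zero. As written, an analysis of all implanted subjects cannot be built for explant under either reading.

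**The case against.** The strongest reply is that the event-type reading is the natural one. The sentence attaches fatality to events, not to subjects. The plan uses the same verb loosely elsewhere: the next paragraph of Section 11.3.2 says that "structural dysfunction will be stratified by the nature of the dysfunction", Section 11.1 speaks of stratifying hemorrhage into major and minor, and Section 11.4 stratifies by NYHA class at each visit. The clause about subjects requiring explant or reoperation may only settle which date counts when there are several. If it restricted the risk set, the valve-size curves would fall to 0% as well, which nobody can intend.

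Most of this stands. A reader might infer that the planned curves are meaningless, or that freedom from reoperation and explant will go unestimated. The documents do not support either. The first is true only of the literal reading. As to the second, Section 4.2.2 lists both outcomes for actuarial analysis, and Section 11.3.1 plans Kaplan-Meier freedom from each adverse event, whatever this sentence means.

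Two things do not stand. The parallel usages concern frequencies, rates and tabulations, where a split by event type leaves the denominator intact; in Kaplan-Meier the stratum sets the risk set, so the usage does not carry over safely. It may also be said that event-type Kaplan-Meier would suffice and that cumulative incidence is a matter of taste. Event-type Kaplan-Meier is interpretable, but as a risk in the absence of death. As the share of patients who will have the event it is too high, by more than a quarter here.

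**Conclusion.** The point holds as an ambiguous specification with two consequences. Taken literally, the split produces curves that end at 0% and do not estimate freedom from the event. Taken as event types, it produces usable curves, but their complements overstate each type's 8-year risk by a factor of about 1.3 (6.9% against 5.4% for non-fatal reoperation in the central case). That factor rests on the plan's 60% survival, constant hazards and complete follow-up. The absolute figures rest on assumed reoperation rates and fatal shares.

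The importance is modest. The breakdown is descriptive and secondary. The primary safety and effectiveness tests, the sample size and the overall freedom-from-event curves do not depend on it. With perhaps 0 to 5 fatal events expected, the fatal curve will be imprecise by any method. The explant time origin is a separate slip in the same paragraph and should be corrected with it.

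**What to change.** Replace the sentence on fatal and non-fatal events with: *Fatal and non-fatal reoperation, and fatal and non-fatal explant, will be reported as separate event types in all implanted subjects, as cumulative incidence from the date of implant, with the other type and death without the event as competing events.*

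State in advance what makes a reoperation or explant fatal, for example death within a stated window. The 30 days in Section 10.4 is not such a definition. It does bear on the choice, because Section 10.5 allows a subject to leave the study 30 days after explant, so deaths beyond that point may not be captured.

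In the same paragraph, change the time origin for explant from reoperation to implant. Keep the overall Kaplan-Meier curves and the valve-size strata.

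The cost is two edited sentences, one definition and a little extra programming. No new data are needed if the definition stays within the period in which deaths are already reported. The intervals for the fatal type will be wide, and the report should say so.
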